9.2.3 Study population

The study population will be drawn from the HRI database which comprises approximately 4 million covered lives in 2013 on an anonymized case-by-case individual level. Almost 80% of the insured individuals in the database are observable for the entire available observation period of up to six years (most currently from 2010 to 2015). This sample represents 4.8% of the German population and 5.6% of the German SHI population. The insured individuals are distributed all over Germany and the database is already structured to be representative for the German population in terms of age and gender (structure of age and gender as per 31.12.2013 / DESTATIS).

This subset of patients will be used for the purposes of this study. Since this study will use only de-identified patient records and will not involve the collection, use, or transmittal of individually identifiable data, institutional review board approval is not required.

The study population will consist of incident Rivaroxaban or Phenprocoumon users with NVAf in the enrollment period spanning from 1 January 2012 through 31 December 2015.

Figure 1. Selection of the study population

9.3 Variables

9.3.1 Baseline characteristics

Baseline period:

365 days prior to index date for hospital diagnoses and prescriptions and four quarters prior to the index quarter for ambulatory diagnosis. This period will be used to determine whether patients have an NVAF diagnosis, to verify that patients are new users and to assess baseline demographic and clinical characteristics of the patients included in the study population.

The following demographics will be reported for each cohort:

- Gender
- Age
- Age group
 - 18-65, 65-74, ≥ 75

The following clinical characteristics will be reported for each cohort:

- 4-quarter Charlson comorbidity index (CCI)
- CKD, which is important as risk of adverse events among patients receiving NOACs tends to differ according to renal function)
- CHADS₂ score, including Congestive heart failure, hypertension, age, diabetes, stroke
- CHA₂DS₂-Vasc score
- HASBLED score, as measurable without lab values
- Prior non-CNS systemic embolism
- Prior oral anticoagulant use (expected to be 0 with 180-day covariate look back)
- Other relevant co-morbidities:
 - Congestive heart failure
 - DVT
 - Essential hypertension
 - Diabetes mellitus
 - Pulmonary embolism
 - Unstable angina
 - Hyperthyroidism
 - Functional dyspepsia
 - Renal failure

- Other cardiovascular drugs:
 - Antiarrhythmics
 - Beta blockers
 - ACE inhibitors
 - ARBs
 - Calcium channel blockers
 - Diuretics
 - Anti-platelet drug classes
 - NSAIDS

Stroke risk score CHADS₂ and CHA₂DS₂-VASc

Stroke risk scores in the individual pre-index period of 4 quarters before the index quarter with defined risk factors and corresponding ICD-10-GM codes including heart failure, hypertension, age groups, diabetes mellitus, stroke/TIA/embolism, vascular disease and gender (listed in Annex 2, Table 7).

To include Health Care Proxies

- Number of hospitalizations in the baseline period
- Number of unique medications in the baseline period

Comorbidities

Presence of relevant comorbidities e.g. hemorrhagic diathesis due to anticoagulants and antibodies, coagulopathy, hyperthyroidism, etc. (see Annex 2, Table 6) in the inpatient sector (main and secondary diagnoses) or in the outpatient sector (verified diagnoses and in addition “condition after diagnoses” for stroke, bleedings and MI) in the patient’s medical history in the individual pre-index period of 4 quarters before the index quarter will be assessed.

Co-medications

Prescription medications of relevant comedications including anticoagulation therapy, antiarrhythmic drugs, and other medications (see Annex 2, Table 13) in the individual 4 quarters before the index quarter (pre-index period) will be assessed.

Table 2 – Definition of covariates

Variable	Category	Operational definition
Age	continuous	Age in the index quarter.
Gender	categorical	Sex on the index date.

Insurance status	categorical	
Insurance status on the index date:
 
 • regular insurance • retired • family insured • unknown
Number of hospitalizations	continuous	Total number of hospitalizations, independent of admission diagnosis, during the baseline period.
No of unique medications	continuous	Number of unique pharmaceutical substances (unique ATC 5 Codes) per patient received during the baseline period, based on the prescriptions documented in the database.
Interactions with co-medications	categorical	
In order to determine whether patients were concurrently treated with other medication interacting with Rivaroxaban or Phenprocoumon, it will be assessed whether patients received any of the relevant substances in the 90 days before the Index date.
 
For a list of medications with interaction potential see Table 12.

CHA ₂ DS ₂ -VASc Score	continuous	
The CHA₂DS₂-VASc score will be derived by assigning one point each for hypertension, diabetes mellitus, and heart failure, vascular disease (peripheral artery disease, myocardial infarction, aortic plaque), age 65-74 years, female sex and two points for age 75 years or older, previous stroke or transient ischemic attack (TIA), with a total possible score of nine [Trappe 2012].
 
Ambulatory verified as well as primary and secondary hospital discharge diagnoses within in the 12 months before the index date will be used to assess the CHA₂DS₂-VASc score.
 
For a complete list of all ICD-10 codes which will be used to form the CHA₂DS₂-VASc score please refer to Annex 2. Tables.


CHADS₂ Score
	
continuous
	
The CHADS₂ Score will be derived by assigning one point each for hypertension, heart failure, age 75 years and older, diabetes mellitus. A preliminary stroke/TIA will be assigned two points, with a total possible score of six [Trappe 2012].
 
Ambulatory verified as well as primary and secondary hospital discharge diagnoses within in the 12 months before the Index date will be used to assess the CHADS₂ score.
 
For a complete list of all ICD-10 codes which will be used to form the CHADS₂ score please refer t to Annex 2. Tables.

Charlson Comorbidity Index (CCI)
	
continuous
	
The Charlson Comorbidity Index (CCI) will be used to weigh comorbidities in the baseline period depending on their severity.
 
Ambulatory verified as well as primary and secondary hospital discharge diagnoses within the 12 months before the index date will be used to build the CCI score. A list of included conditions and their assigned weights can be found in Annex 2. Tables.
 
Please consider the following publications for further information regarding the applied methodology:
 

Comorbidity Index (modified Charlson Comorbidity Index)	continuous	
In order to avoid a high degree of correlation between some covariates a separate Comorbidity Index was defined, which includes only disease categories which are not already measured by the HAS BLED score.
 
This modified Comorbidity Index contains all Charlson disease categories except hypertension, congestive heart failure, cerebrovascular disease, mild, moderate or severe liver disease and moderate or severe renal disease.

Bleeding history (modified HAS BLED Score)	continuous	
The HAS-BLED score is derived for each patient in the baseline period by assigning one point and summing the score across the following conditions: hypertension, renal disease, cirrhosis, and stroke, major bleeding event, age 65 and older, use of non-steroidal anti-inflammatory drug, intake of antiplatelet agents, alcohol abuse.
 
Since the HRI database does not contain any laboratory parameters, the international normalized ratio (INR) will not be included in the HAS-BLED score.
 
For a complete list of all ICD codes which will be used to form the HAS-BLED score please refer to Annex 2. Tables.

Myocardial infarction (MI)	categorical	
Ambulatory verified diagnoses in the four quarters prior to the index quarter as well as primary and secondary hospital discharge diagnoses within the 365 days before or on the index date will be used to assess whether patients suffered from a previous myocardial infarction. MI will be defined using the ICD-10 GM code I21.* and I22.*.

Chronic renal insufficiency	categorical	
Ambulatory verified diagnoses in the four quarters prior to the index quarter as well as primary and secondary hospital discharge diagnoses within the 365 days before or on the index date will be used assess whether patients suffered from a chronic renal insufficiency. Chronic renal insufficiency will be defined using the ICD-10 GM code N18.*.

Chronic renal insufficiency stage I	categorical	Ambulatory verified diagnoses in the four quarters prior to the index quarter as well as primary and secondary hospital discharge diagnoses within the 365 days before or on the index date will be used assess whether patients suffered from a chronic renal insufficiency, stage I. Chronic renal insufficiency, stage I will be defined using the ICD-10 GM code N18.1.
Chronic renal insufficiency stage II	categorical	Ambulatory verified diagnoses in the four quarters prior to the index quarter as well as primary and secondary hospital discharge diagnoses within the 365 days before or on the index date will be used assess whether patients suffered from a chronic renal insufficiency, stage I. Chronic renal insufficiency, stage II will be defined using the ICD-10 GM code N18.2.
Chronic renal insufficiency stage III	categorical	Ambulatory verified diagnoses in the four quarters prior to the index quarter as well as primary and secondary hospital discharge diagnoses within the 365 days before or on the index date will be used assess whether patients suffered from a chronic renal insufficiency, stage I. Chronic renal insufficiency, stage III will be defined using the ICD-10 GM code N18.3.
Chronic renal insufficiency stage IV	categorical	Ambulatory verified diagnoses in the four quarters prior to the index quarter as well as primary and secondary hospital discharge diagnoses within the 365 days before or on the index date will be used assess whether patients suffered from a chronic renal insufficiency, stage I. Chronic renal insufficiency, stage IV will be defined using the ICD-10 GM code N18.4.
Chronic renal insufficiency stage V	categorical	Ambulatory verified diagnoses in the four quarters prior to the index quarter as well as primary and secondary hospital discharge diagnoses within the 365 days before or on the index date will be used assess whether patients suffered from a chronic renal insufficiency, stage I. Chronic renal insufficiency, stage V will be defined using the ICD-10 GM code N18.5.

Other chronic renal insufficiency	categorical	Ambulatory verified diagnoses in the four quarters prior to the index quarter as well as primary and secondary hospital discharge diagnoses within the 365 days before or on the index date will be used assess whether patients suffered from other chronic renal insufficiency. Other chronic renal insufficiency will be defined using the ICD-10 GM code N18.8.
Unspecified chronic renal insufficiency	categorical	Ambulatory verified diagnoses in the four quarters prior to the index quarter as well as primary and secondary hospital discharge diagnoses within the 365 days before or on the index date will be used assess whether patients suffered from an unspecified renal insufficiency. Unspecified chronic renal insufficiency will be defined using the ICD-10 GM code N18.9.
Diabetes	categorical	Ambulatory verified diagnoses in the four quarters prior to the index quarter as well as primary and secondary hospital discharge diagnoses within the 365 days before or on the index date will be used assess whether patients suffered from diabetes mellitus. Diabetes mellitus will be defined using the ICD-10 GM code E10.*-E14.*.
Hypertension	categorical	Ambulatory verified diagnoses in the four quarters prior to the index quarter as well as primary and secondary hospital discharge diagnoses within the 365 days before or on the index date will be used assess whether patients suffered from hypertension. Hypertension will be defined using the ICD-10 GM code I10.*.
Congestive heart failure	categorical	Ambulatory verified diagnoses in the four quarters prior to the index quarter as well as primary and secondary hospital discharge diagnoses within the 365 days before or on the index date will be used assess whether patients suffered from congestive heart failure. Congestive heart failure will be defined using the ICD-10 GM code I50.*.

Atherosclerosis of arteries of extremities	categorical	Ambulatory verified diagnoses in the four quarters prior to the index quarter as well as primary and secondary hospital discharge diagnoses within the 365 days before or on the index date will be used assess whether patients suffered from peripheral vascular disease. Peripheral vascular disease will be defined using the ICD-10 GM code I70.2.
Ischemic stroke or TIA during baseline	categorical	Ambulatory verified diagnoses in the four quarters prior to the index quarter as well as primary and secondary hospital discharge diagnoses within the 365 days before or on the index date will be used assess whether patients suffered from ischemic stroke or TIA. Ischemic stroke or TIA will be defined using the ICD-10 GM code I63, I64, G45.9 and G45.8.
Coronary heart disease	categorical	Ambulatory verified diagnoses in the four quarters prior to the index quarter as well as primary and secondary hospital discharge diagnoses within the 365 days before or on the index date will be used assess whether patients suffered from coronary heart disease. Coronary heart disease will be defined using the ICD-10 GM code I20*(angina pectoris), I24.*(other acute ischemic heart diseases) and I25* (chronic ischaemic heart disease).
Liver disease		
Mild liver disease	categorical	Ambulatory verified diagnosis in the four quarters prior to the index quarter as well as primary and secondary hospital discharge diagnoses within the 365 days before or on the index date will be used assess whether patients suffered from a mild liver disease. Mild liver disease will be defined using the ICD-10 GM codes according to the Charlson Comorbidity Index (Table 8).

Moderate or severe liver disease	categorical	
Ambulatory verified diagnosis in the four quarters prior to the index quarter as well as primary and secondary hospital discharge diagnoses within the 365 days before or on the index date will be used assess whether patients suffered from a moderate or severe liver disease. Moderate or severe liver disease will be defined using the ICD-10 GM codes according to the Charlson Comorbidity Index (Table 8).

Severe liver disease	categorical	
Ambulatory verified diagnosis in the four quarters prior to the index quarter as well as primary and secondary hospital discharge diagnoses within the 365 days before or on the index date will be used assess whether patients suffered from a severe liver disease. Severe liver disease will be defined using the ICD-10 GM codes
 
K70.4 Alcoholic hepatic disease K71.1 Toxic liver disease with hepatic necrosis K72.1 Chronic hepatic failure K72.9 Hepatic failure, unspecified K76.5 Hepatic veno-occlusive disease K76.6 Portal hypertension K76.7 Hepatorenal syndrome I85.0 Oesophageal varices with bleeding I85.9 Oesophageal varices without bleeding I86.4 Gastric varices I98.2 Oesophageal varices without bleeding in diseases classified elsewhere

Smoking	categorical	
Ambulatory verified diagnosis in the four quarters prior to the index quarter as well as primary and secondary hospital discharge diagnoses within the 365 days before or on the index date will be used assess whether patients used tobacco. Tobacco use will be defined using the ICD-10 GM codes F17.*, Z71.6, Z72.0.

Alcohol abuse	categorical	Ambulatory verified diagnosis in the four quarters prior to the index quarter as well as primary and secondary hospital discharge diagnoses within the 365 days before or on the index date will be used assess whether patients abused alcohol. Alcohol abuse will be defined using the ICD-10 GM codes F10.*, Z71.4, Z50.2, Z72.1.
Depression	categorical	Ambulatory verified diagnosis in the four quarters prior to the index quarter as well as primary and secondary hospital discharge diagnoses within the 365 days before or on the index date will be used assess whether patients suffered from depression. Depression will be defined using the ICD-10 GM codes F32*, F33.*, F34.1.
Somatoform disorder	categorical	Ambulatory verified diagnosis in the four quarters prior to the index quarter as well as primary and secondary hospital discharge diagnoses within the 365 days before or on the index date will be used assess whether patients suffered from somatoform disorder. Somatoform disorder will be defined using the ICD-10 GM codes F45.*.
Anxiety disorder	categorical	Ambulatory verified diagnosis in the four quarters prior to the index quarter as well as primary and secondary hospital discharge diagnoses within the 365 days before or on the index date will be used assess whether patients suffered from anxiety disorder. Anxiety disorder will be defined using the ICD-10 GM codes F40.* and F41.*.
Substance abuse	categorical	Ambulatory verified diagnosis in the four quarters prior to the index quarter as well as primary and secondary hospital discharge diagnoses within the 365 days before or on the index date will be used assess whether patients suffered from substance abuse. Substance abuse will be defined using the ICD-10 GM codes F11*, F12*, F13*, F14*, F15*, F16*, F18*, F19*.

Dementia	categorical	Ambulatory verified diagnosis in the four quarters prior to the index quarter as well as primary and secondary hospital discharge diagnoses within the 365 days before or on the index date will be used assess whether patients suffered from dementia. Dementia will be defined using the ICD-10 GM codes F00, F01, F02, F03.
Cancer	categorical	Ambulatory verified diagnosis in the four quarters prior to the index quarter as well as primary and secondary hospital discharge diagnoses within the 365 days before or on the index date will be used assess whether patients suffered from cancer. Cancer will be defined using the ICD-10 GM code C*.
Obesity	categorical	Ambulatory verified diagnosis in the four quarters prior to the index quarter as well as primary and secondary hospital discharge diagnoses within the 365 days before or on the index date will be used assess whether patients suffered from obesity. Obesity will be defined using the ICD-10 GM codes E66.
Proton-pump-inhibitors (omeprazol)	categorical	It will be assessed whether patients received at least one prescription for proton-pump-inhibitors in the 365 days before or on the index date. For a complete list of all relevant ATC Codes please refer to Table 13.
Coronary angioplasty	categorical	It will be assessed whether patients underwent a percutaneous transluminal coronary angioplasty (PTCA) in the 365 days before or on the index date. The OPS Code 8837 (perkutan-transluminale Gefäßintervention an Herz und Koronargefäßen) will be used to determine whether the procedure has been performed in the patient individual baseline period.
Antiplatelet medication	categorical	It will be assessed whether patients received at least one prescription for antiplatelet medications in the 365 days before or on the index date. The relevant ATC code that will be used is B01AC.

Prescription of acetylsalicylic acid (ASS)	categorical	It will be assessed whether patients received at least one prescription for ASS (ATC Code: B01AC06) in the 365 days before or on the index date.
Prescription of non-steroidal anti-inflammatory drugs (NSAIDs)	categorical	It will be assessed whether patients received at least one prescription for NSAIDs (ATC Code: M01A*) in the 365 days before or on the index date.

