XARELTO 20 mg Filmtabletten	98	St	10072124
XARELTO 20 mg Filmtabletten	98	St	10852709
XARELTO 20 mg Filmtabletten	98	St	10393644
XARELTO 20 mg Filmtabletten	98	St	4369498

XARELTO 20 mg Filmtabletten	98	St	10200929
XARELTO 20 mg Filmtabletten	98	St	10743802
XARELTO 20 mg Filmtabletten	98	St	10382008
XARELTO 20 mg Filmtabletten	98	St	10999364
XARELTO 20 mg Filmtabletten	98	St	11096612
XARELTO 20 mg Filmtabletten	98	St	11559354
XARELTO 20 mg Filmtabletten	100	St	9333401
XARELTO 20 mg Filmtabletten	10X10	St	9941299

Table 5 – Definition of types of AF

Type of AF	ICD-10-GM code
Paroxysmal	I48.0
Persistent	I48.1
Permanent	I48.2
Typical	I48.3
Atypical	I48.4
Unknown	I48.9

Table 6 – Definition of primary and secondary outcomes

Outcome parameter	ICD-10 GM code	
Primary effectiveness: ischemic stroke	I630, I631, I632, I633, I634, I635, I636, I638, I639	
Primary safety: Intracranial hemorrhage (ICH)	I60.0, I60.1, I60.2, I60.3, I60.4, I60.5, I60.6, I60.7, I60.8, I60.9, I61.0, I61.1, I61.2, I61.3, I61.4, I61.5, I61.6, I61.8, I61.9, I62.00, I62.01, I62.02, I62.09, I62.1, I62.9	
Secondary	combined endpoint cerebral benefit	ischemic stroke and ICH
	systemic embolism (SE) (effectiveness)	I26, I260, I269, I801, I802, I803, I809
	transient ischemic attack (TIA) (effectiveness)	G45.8, G45.9
	combined endpoint effectiveness	ischemic stroke, systemic embolism (SE) and transient ischemic attack (TIA)
	subarachnoid hemorrhage (safety)	I60.0, I60.1, I60.2, I60.3, I60.4, I60.5, I60.6, I60.7, I60.8, I60.9
	intracerebral hemorrhage (safety)	I61.0, I61.1, I61.2, I61.3, I61.4, I61.5, I61.6, I61.8, I61.9
	other and unspecified nontraumatic intracranial hemorrhage (safety)	I62.00, I62.01, I62.02, I62.09, I62.1, I62.9

Table 7 – Definition of stroke risk score CHADS₂ and CHA₂DS₂-VASc

Risk factor	CHADS₂ risk score value	CHA₂DS₂-VASc risk score value	ICD-10-GM code	Description
Heart failure	1	1	I50	Heart Failure
Hypertension	1	1	I10	Essential (primary) hypertension
Age 65-74 years	0	1	-	
Age ≥75 years	1	2	-	

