Diabetes mellitus	1	1	E11/E10/ E12	Type 2 diabetes mellitus/ Type 1 diabetes mellitus/ Diabetes mellitus in combination with malnutrition Non-traumatic intracerebral hemorrhage/ Cerebral infarction/stroke/ Sequelae of cerebrovascular disease/ Other venous embolism and thrombosis/ Transient cerebral ischemic attacks and related syndromes/ Arterial embolism and thrombosis/ Acute vascular disorders of intestine/ Ischemia and infarction of kidney/ Retinal vascular occlusions Acute myocardial infarction/ recurrent myocardial infarction/ Certain current complications following myocardial infarction/ Other peripheral vascular diseases
Stroke/TIA/embolism	2	2	I61/I63/I64/ I69/I82/G45 /I74/K55.0/ N28.0/H34	
Vascular disease (prior myocardial infarction/peripheral artery disease/aortic plaque)	0	1	I21/I22/I23/ I73	
Female gender	0	1	-	

Table 8 – Comorbidities included in the Charlson Comorbidity Index (CCI) and modified comorbidity index

Conditions	ICD-10 GM code	Assigned weights CCI	Assigned weights modified comorbidity index
Myocardial Infarction	I21, I22, I252	1	1
Congestive heart failure	I43, I50, I099, I110, I130, I132, I255, I420, I425, I 426, I427, I428, I429, P290	1	0
Peripheral vascular disease	I70, I71, I731, I738, I739, I771, I790, I792, K551, K558, K559, Z958, Z959	1	1
Cerebrovascular disease	G45, G46, I60, I61, I62, I63, I64, I65, I66, I67, I68, I69, H340	1	0
Dementia	F00, F01, F02, F03, G30, F051, G311	1	1
Chronic pulmonary disease	J40, J41, J42, J43, J44, J45, J46, J47, J60, J61, J62, J63, J64, J65, J66, J67, I278, I279, J684, J701, J703	1	1
Connective tissue disease	M05, M32, M33, M34, M06, M315, M351, M353, M360	1	1
Ulcer disease	K25, K26, K27, K28	1	1
Mild liver disease	B18, K73, K74, K700, K701, K702, K703, K709, K717, K713, K714, K715, K760, K762, K763, K764, K768, K769, Z944	1	0
Diabetes	E100, E101, E106, E108, E109, E110, E111, E116, E118, E119, E120, E121, E126, E128, E129, E130, E131, E136, E138, E139, E140, E141, E146, E148, E149	1	1
Hemiplegia	G81, G82, G041, G114, G801, G802, G830, G831, G832, G833, G834, G839	2	2
Moderate or severe renal disease	N18, N19, N052, N053, N054, N055, N056, N057, N250, I120, I131, N032, N033, N034, N035, N036, N037, Z490, Z491, Z492, Z940, Z992	2	0
Diabetes with end organ damage	E102, E103, E104, E105, E107, E112, E113, E114, E115, E117, E122, E123, E124, E125, E127, E132, E133, E134, E135, E137, E142, E143, E144, E145, E147	2	2

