Any tumor	C00, C01, C02, C03, C04, C05, C06, C07, C08, C09, C10, C11, C12, C13, C14, C15, C16, C17, C18, C19, C20, C21, C22, C23, C24, C25, C26, C30, C31, C32, C33, C34, C37, C38, C39, C40, C41, C43, C45, C46, C47, C48, C49, C50, C51, C52, C53, C54, C55, C56, C57, C58, C60, C61, C62, C63, C64, C65, C66, C67, C68, C69, C70, C71, C72, C73, C74, C75, C76, C81, C82, C83, C84, C85, C88, C90, C91, C92, C93, C94, C95, C96, C97	2	2
Moderate or severe liver disease	K704, K711, K721, K729, K765, K766, K767, I850, I859, I864, I982	3	0
Metastatic solid tumor or AIDS	C77, C78, C79, C80, B20, B21, B22, B24	6	6

Table 9 – Operationalization HAS-BLED Score

Criteria	ICD-10 GM code
Hypertension	I10.*, I11.*, I12.*, I13.*, I14.*, I15.*
Renal disease	N18.*, N19.*
Cirrhosis	K70.3, K71.7, K74.*
Stroke	I63.*
Major bleeding event	Primary or secondary hospital discharge of ICD-10 codes as listed in Table 11
Alcohol use	F10.*
Non-steroidal anti-inflammatory drug	M01A*
Antiplatelet agents	B01AC*
Age >65	

Table 10 – Definition of comorbidities

Comorbidity	ICD-10-GM code / OPS Code
Hemorrhagic diathesis due to anticoagulants and antibodies	D68.3
Coagulopathy, not specified	D68.9
Hyperthyroidism	E05
Diabetes mellitus	E10-E14
Hyperlipidemia	E78.0-E78.5
Cerebral transitory ischemia and related problems	G45
Essential hypertension	I10
Angina pectoris	I20
Myocardial infarction	I21-I22
Other acute ischaemic heart disease	I24
Chronic ischaemic heart disease	I25
Pulmonary embolisms	I26
Heart failure	I50
Intracerebral hemorrhage	I61
Other non-traumatic intracranial bleeding	I62
Cerebral infarction	I63
Stroke, not referred to as bleeding or infarction	I64
Hemorrhage or intracranial bleeding or cerebral infarction or stroke	I61-I64
Peripheral vascular disease, not specified	I73.9
Embolism and thrombosis of unspecified artery	I74.9
Deep thrombosis on leg and pelvic veins	I80-I82 without I80.0
Functional dyspepsia	K30
Hepatic insufficiency	K72
Renal insufficiency	N17-N18
Chronic renal disease, stage 1	N18.1
Chronic renal disease, stage 2	N18.2
Chronic renal disease, stage 3	N18.3
Chronic renal disease, stage 4	N18.4
Chronic renal disease, stage 5	N18.5
Cancer	C00-C97
Gastrointestinal bleeding*	K92.0.-K92.2
Dialysis	Z49.0, Z49.1, Z49.2
Hip or knee replacement procedure	OPS 5820, OPS 5821, OPS 5822, OPS 5823

Table 11 – Definition of major bleeding events for HAS-BLED Score

Primary or secondary hospital discharge diagnosis ICD-10-GM code	ICD-10-GM code

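### The hypertension and heart-failure flags and the stroke-score components use narrower codes than the protocol's own HAS-BLED and CCI lists, and the modified index drops heart failure on a mistaken ground

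*Protocol*

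**What the plan says.** All places are in the protocol.

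- **Hypertension.** Table 2 (section 9.3.1): "Hypertension will be defined using the ICD-10 GM code I10". Table 7 (stroke scores) uses I10, described as "Essential (primary) hypertension", and Table 10 (comorbidities) also uses I10. Table 9 (HAS-BLED) uses "I10.*, I11.*, I12.*, I13.*, I14.*, I15".
- **Congestive heart failure.** Table 2: "Congestive heart failure will be defined using the ICD-10 GM code I50". Tables 7 and 10 also use I50. Table 8 (CCI) lists "I43, I50, I099, I110, I130, I132, I255, I420, I425, I 426, I427, I428, I429, P290", with weight 1 in the CCI and weight 0 in the modified comorbidity index.
- **Modified comorbidity index.** Table 2 describes it as an index "which includes only disease categories which are not already measured by the HAS BLED score", and names congestive heart failure among the categories left out.
- **Use in the models (section 9.7.1.2).** The propensity score takes every measured factor without selection. The adjusted Cox model takes a subset of Table 2 that is chosen empirically and not named.
- **No later document.** Section 9.7 says there will be no separate SAP.

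**The concern.** The comparison is not randomised, so it depends on measured covariates to control confounding. Hypertension and heart failure are components of the protocol's own stroke scores and are therefore confounders that the design means to control. The protocol gives no reason for counting the same patient as hypertensive, or as having heart failure, in one variable and not in another.

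Where the narrow list applies, a patient who carries only a wider code is grouped with patients who do not have the condition. The rationale for the modified index makes this worse for heart failure: it treats the condition as already covered by a score that has no item for it. The stake is avoidable residual confounding by stroke risk in the adjusted and matched hazard ratios.

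**Working it through.** The protocol gives no figure to reproduce. The check sets the code lists side by side and follows them into the models.

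**Step 1. Code lists**

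| Condition | Table 2 flag | Table 7 scores | Table 10 | Wider list |
|---|---|---|---|---|
| Hypertension | I10 | I10 | I10 | Table 9: I10 to I15 |
| Heart failure | I50 | I50 | I50 | Table 8: 14 codes |

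**Step 2. Codes missed by the narrow lists**

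- Hypertension: 6 − 1 = 5 categories, namely I11, I12, I13, I14 and I15.
- Heart failure: 14 − 1 = 13 codes, namely I09.9, I11.0, I13.0, I13.2, I25.5, I42.0, I42.5 to I42.9 (five codes), I43 and P29.0.

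**Step 3. How a patient with a single wider code is scored**

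| Only code | Hypertension flag | Heart-failure flag | Hypertension + heart-failure points, each stroke score | HAS-BLED hypertension | CCI heart failure | Modified index heart failure | Coronary flag (I20, I24, I25) |
|---|---|---|---|---|---|---|---|
| I11.0 | 0 | 0 | 0 | 1 | 1 | 0 | 0 |
| I15 | 0 | 0 | 0 | 1 | 0 | 0 | 0 |
| I25.5 | 0 | 0 | 0 | 0 | 1 | 0 | 1 |
| I42.0 or I43 | 0 | 0 | 0 | 0 | 1 | 0 | 0 |

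Under the wider lists the I11.0 patient would score 1 + 1 = 2 points for these two items, against 0 as written: a loss of 2 on both CHADS2 (maximum 6) and CHA2DS2-VASc (maximum 9). The I15, I25.5 and I42.0/I43 patients each lose 1.

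**Step 4. The ground for dropping heart failure from the modified index**

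The HAS-BLED items in Table 2 and Table 9 are hypertension, renal disease, cirrhosis, stroke, major bleeding, age, NSAIDs, antiplatelet agents and alcohol. None is heart failure, so the stated reason for weight 0 does not hold for that category. The same sentence also excludes hypertension, which is not a category in Table 8, so the exclusion list does not match the tables it refers to.

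**Step 5. What each model sees**

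- *Propensity score.* HAS-BLED and the CCI are Table 2 covariates, so they enter beside the narrow flags. Codes I11 to I15 move HAS-BLED by one point and the 13 heart-failure codes move the CCI by one. Both are totals, and balance on a total does not ensure balance on one component.
- *Cox model.* If the chosen subset contains the modified index and not the CCI, the last row of the Step 3 table has no entry other than 0. I11.0, I13.0 and I13.2 can still register through HAS-BLED, and I25.5 through the coronary flag, if those covariates are selected, but not as heart failure.
- *Balance table.* The Table 30 shell names CHA2DS2-VASc and separate comorbidities, which rest on the narrow codes. It does not name HAS-BLED or the CCI.

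**The case against.** The narrow definitions are applied consistently as single-condition flags in Tables 2, 7 and 10. The wider lists appear only inside composite scores, and for the CCI the protocol cites a published coding algorithm. A score component need not match a stand-alone flag. This has some force: a difference alone is not an error. But the protocol does not explain the difference, and Table 2 already takes its mild and its moderate or severe liver disease flags from Table 8. It also does not answer the mistaken rationale for the modified index.

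Three stronger readings are tempting, and the documents do not support them.

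- *These patients enter the whole adjustment as free of disease.* They do not. With all measured factors in the propensity score, HAS-BLED, the CCI and, for I25.5, the coronary flag keep part of the information. Complete loss is confined to the Cox model, and only under a covariate choice that the protocol neither states nor rules out.
- *Previous MI has the same problem.* Table 2 says "MI will be defined using the ICD-10 GM code I21.* and I22", while Table 8 adds I25.2. But I25.2 already sets the coronary heart disease flag and has weight 1 in both the CCI and the modified index, so little is lost.
- *A count of misclassified patients can be given.* No code frequencies are reported, and a patient who also carries I10 or I50 is unaffected for that condition.

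**Conclusion.** The point holds for hypertension and heart failure. As written, the lists set the flags and the stroke-score points to 0 for patients whom the protocol counts elsewhere as having the condition. Per patient, the size is one point on each stroke score for a single missed condition and two for I11.0 alone. In the propensity score the loss is partial. In the Cox model it can be complete for heart failure coded only as I42.0, I42.5 to I42.9 or I43, on the assumption that the modified index is selected and the CCI is not.

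The number of such patients and the direction and size of any bias in the hazard ratios cannot be derived from the protocol. This is an avoidable weakness in confounder measurement that should be corrected; it does not show that the planned comparison is invalid.

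**What to change.** 1. In Tables 2, 7 and 10, define hypertension as I10 to I15 (as in Table 9) and heart failure by the Table 8 list. Alternatively, keep the narrow lists and state why they differ.
2. Correct the rationale for the modified index. With the widened flag in the model, say that heart failure is captured by that flag and leave its weight at 0. If the flag is not in the model, restore weight 1. Do not do both: heart failure would count twice, and the index exists to avoid correlated covariates. Remove hypertension from the list of excluded Charlson categories, since Table 8 has none.
3. Settle this before the Cox covariates are selected.

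The cost is a set of code-list edits in Table 2 and Annex 2, with no new data. The small downside is that the scores become slightly less comparable with work that used I10 and I50 only.
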